13.2.4 Electronic and Central Data Validation

SecuTrial® includes among others Audit-Trial, electronic signature, programmable tests of plausibility, consistency and value range, a query management system for online monitoring and a customizable system to assign roles and authorizations. Details for the software and its functionalities are described in separate documents which can be provided on request. The CTC will perform checks of accumulating study data. These are performed regularly through the study, and include range, plausibility, and consistency checks.

13.3 Monitoring

Regular monitoring visits at the investigator's site prior to the start and during the course of the study will help to follow up the progress of the clinical study, to assure utmost accuracy of the data and to detect possible errors at an early time point. The Sponsor-Investigator organises professional independent monitoring for the study.

All original data including all patient files, progress notes and copies of laboratory and medical test results must be available for monitoring. The project monitor, located at the CTC Zurich, will perform monitoring according to national laws and guidelines and the specifications of the ICH-GCP guidelines. The CTC project monitor will visit study sites at regular intervals to monitor the execution of the study. They will have access to all documents that are needed to perform their task according to the above mentioned guidelines. The CTC project monitor will check whether requirements to conduct the study are met and study procedures are followed correctly, and will check the study site's documentation, the participants' source data, eCRF entries, and the correct maintenance of the Investigator Site File. The monitor will review all or a part of the eCRFs and written informed consents. The accuracy of the data will be verified by reviewing the above referenced documents. The investigator's site will collaborate with the Clinical Trials Center (CTC) of the University Hospital Zurich to ensure regular monitoring. According to the CTC's Monitoring SOP the extent and nature of monitoring activities based on the objective and design of the study will be defined in a study specific Monitoring Plan.

13.4 Audits and Inspections

A quality assurance audit/inspection of this study may be conducted by the competent authority or CEC, respectively. The quality assurance auditor/inspector will have access to all medical records, the investigator's study related files and correspondence, and the informed consent documentation that is relevant to this clinical study.

The investigator will allow the persons being responsible for the audit or the inspection to have access to the source data/documents and to answer any questions arising. All involved parties will keep the patient data strictly confidential.

13.5 Confidentiality, Data Protection

Direct access to source documents will be permitted for purposes of monitoring, audits and inspections. Privacy laws and regulations will be adhered to during all procedures related to this study. The collection and processing of participants' personal information will be limited to what is necessary to insure the study's scientific practicability and to assess the research questions. Information collected about participants during this clinical investigation will be treated confidentially. The local investigator or her/his co-workers will collect data and transfer it without recording the subject's name or date of birth, but coded with a subject identification code. Therefore, data is not directly traceable to individual subjects. A subject identification code links the data to the individual subject.

The code will be safeguarded by the data manager of the CTC Zürich; the key to this subject identification code will be kept at the CTC (via SecuTrial®). The emergency unblinding procedure or access to the randomisation code list by the authorities or the IDMC is described above. Anonymous (coded) data can be relayed to the central study team for scientific analysis or made available, if necessary, to the responsible federal supervisory authority (in case of audits during the course of the study).

Only qualified and authorised collaborators of the study sponsor will enter the pseudonymous data into a computerised database. The acquired data will be used without participants' names for scientific analysis. Participants' names will not be mentioned in any publication of study results. Persons monitoring the data will have access to all information needed to ensure the validity of the study data, and are required to keep information confidential as well as to respect data privacy. Participants have the right to look into their data and can check their data in accordance with the relevant judicial regulations and procedures.

13.6 Storage of Biological Material and Related Health Data

A tissue repository (BioBank) will be established in accordance with the HFG/KlinV/HFV. In a separate consent form, subjects will be asked to provide blood for BioBanking in accordance with the Swiss legal regulations. If subjects do not want to have their blood samples stored, they can still participate in the study.

14 PUBLICATION AND DISSEMINATION POLICY

After the statistical analysis of this trial the sponsor will make every endeavour to publish the data in a medical journal. A Publications Committee (applicants, co-applicants, others) will be formed and establish a publication guideline. The scientific integrity of the project requires that the data from all omega-3-pMDD study sites will be analyzed and reported as such (whatever outcome the omega-3 pMDD Study will have). An individual center is not expected to report the data collected from its center alone. All presentations and publications are expected to protect the integrity of the major objective(s) of the study; Data that the IDMC potentially generates will not be presented prior to the release of mainline results. Recommendations as to the timing of presentation of such endpoint data and the meetings at which they might be presented will be given by the Publications Committee. Data will be presented as original papers in key journals. Prior to study commencement, the main and co-applicants will contact different high impact journals (JAMA, Lancet, NEJM) to explore their interest, if they would consider to publish the original key paper once the study is completed and the main publication is finalized. They will be granted access to the protocol after signing a confidentiality agreement in case they want to have some adaptions.

Once the study has commenced, a trials methodology paper will be submitted. Once the recruitment phase has been completed, the demographic data and patient characteristic will be published. Papers will be published alongside the formulated hypothesis. A key responsible researcher will be appointed to drive the data analysis and writing of the paper. The senior researcher is responsible for the establishment of an optimal team of experts to address the key research questions. Each paper or abstract must be submitted to the appropriate Publications committee for review of its appropriateness and scientific merit prior to submission. The final approval is granted by the applicant and co-applicants (which form the publications committee).

Study results will be presented at local, national and international conferences of the field (e.g. Swiss Society of Child and Adolescent annual meeting, the German Society of Child and Adolescent Psychiatry annual meeting, APA, ECNP, IEPA and other conferences).

Reproducibility

No later than 5 years after the collection of the 36-week post-randomisation interviews, we will deliver a completely de-identified data set to an appropriate data archives for sharing purposes.

15 FUNDING AND SUPPORT

15.1 Funding

This study is financed by the Swiss National Science Foundation SNSF (Nr. 33IC30-166826).

15.2 Other Support

The study is also supported by the University of Zurich, Department of Child and Adolescent Psychiatry (Prof. [name]).

16 INSURANCE

Insurance is covered by "Haftpflichtversicherung für den Kanton Zürich betreffend das UniversitätsSpital Zürich" (Policy no.: 14.970.885).

Any damage developed in relation to study participation is covered by this insurance. So as not to forfeit their insurance cover, the participants themselves must strictly follow the instructions of the study personnel. Participants must not be involved in any other medical treatment without permission of the principal investigator (emergency excluded). Medical emergency treatment must be reported immediately to the investigator. The investigator must also be informed instantly, in the event of health problems or other damages during or after the course of study treatment.

The investigator will allow delegates of the insurance company to have access to the source data/documents as necessary to clarify a case of damage related to study participation. All involved parties will keep the patient data strictly confidential.

A copy of the insurance certificate will be placed in the Investigator's Site File.

Omega-3 Fatty Acids as First-Line Treatment in Pediatric Depression

Statistical Analysis Plan for [name], [name]

[name] ([contact])

[name]

Version 1.0 of May 23, 2022

List of abbreviations

AD	antidepressant
AE	adverse event
CDRS-R	Children's Depression Rating Scale - Revised
DIKJ	Children's Depression Inventory (Depressionsinventar für Kinder und Jugendliche)
EPA	eicosapentaenoic acid
KIDscreen-CAT-27	quality of life questionnaire
pMDD	pediatric major depressive disorder
SIQ-Jr	Suicide Ideation Questionnaire-Junior
SUSAR	Suspected Unexpected Serious Adverse Reaction

Introduction

1 Type of trial

This is a 36-week multi-center 1:1 randomized, double-blind, placebo-controlled, two-armed, parallel group study investigating the superiority of EPA-rich Omega-3 to placebo in the treatment of children and adolescents with pediatric major depressive disorder. The randomization included a minimization algorithm based on the following factors: site, age (8-12 vs. 13-18), gender (male vs. female), and hsCRP (<1 mg/l; 1-3 mg/l; >3mg/l). For sites offering both in- and out-patient care, in-/out-patient type was used as an additional minimization factor. The trial aimed to recruit children/teenagers between 8 and 18 years old with a primary diagnosis of major depressive disorder (DSM-IV, K-SADS-PL) and at least moderate depressive symptoms (CDRS-R ≥ 40).

In order to include a representative sample of moderately and severely ill children with major depressive disorders, the use of clinically required SSRIs is permitted. The anticipated proportion of patients receiving additional antidepressants at some point during follow-up is estimated to be around 30%. The use of additional antidepressants is expected to influence primary outcome measurements and be influenced by treatment group, with greater antidepressant use hypothesized in the control arm. Antidepressant use may therefore bias the estimation of the omega-3 treatment effect.

2 Scope of the statistical analysis plan

This statistical analysis plan (SAP) is based on the protocol for the trial SNF 33IC30 166826 "Omega-3 Fatty Acids as First-Line Treatment in Paediatric Depression" version 6 dated 09.03.2021. Its scope is limited to the primary trial objectives, namely efficacy and safety. This SAP includes further details regarding the statistical analysis of the primary and secondary efficacy and safety endpoints to be conducted after closure of the database. Specifically, the following changes were introduced:

- A single primary outcome, longitudinal CDRS-R total score, was selected;
- Remission and response were changed from additional primary outcomes to confirmatory secondary outcomes, while recovery was removed as redundant;
- The scope of the primary trial analysis was reduced, reserving exploration of the relationships between inflammatory and lipid markers and symptoms and treatment response for follow-up analyses described in future analysis plans and manuscripts;
- Further details for statistical analyses per outcome were specified;
- A method assuming MNAR was explicitly specified for the primary analysis of the primary outcome and sensitivity analyses exploring robustness to the selected assumptions were specified.

Changes to the statistical analyses made across protocol versions are documented in the final section of this document.

3 Objectives

The study protocol defines the following study objectives:

1. To investigate the therapeutic efficacy and safety of omega-3 fatty acids rich in EPA in pMDD;
2. to demonstrate clinically meaningful effects of omega-3 fatty acid treatment;
3. to investigate inflammatory and bioactive lipid markers as response predictors;
4. to investigate the relationship between psychopathology (in particular suicidal ideation), illness course and cognition in relation to inflammatory and bioactive lipid markers.

For the purpose of this statistical analysis plan, we focus on the primary trial objectives, i.e., efficacy and safety objectives, as described below.

3.1 Primary objective

- To demonstrate the superiority of daily EPA-rich Omega-3 over placebo as an adjunct to the standard of care (German S3 guidelines) in children and adolescents with pediatric major depressive disorder.

3.2 Secondary objectives

- To demonstrate the clinically meaningful efficacy of daily EPA-rich Omega-3 relative to placebo as an adjunct to the standard of care (German S3 guidelines) in children and adolescents with pediatric major depressive disorder.
- To compare the safety and tolerability of daily EPA-rich Omega-3 versus placebo as an adjunct to the standard of care (German S3 guidelines) in children and adolescents with pediatric major depressive disorder.

4 Estimands

4.1 Primary estimand

Effectiveness (i.e., 'de facto', 'treatment policy') estimand The effectiveness estimand quantifies the average treatment effect of EPA-rich Omega-3 relative to placebo over 36 weeks, as an adjunct to the German S3 guideline standard of care, in all randomized subjects regardless of adherence to treatment or initiation of antidepressants.

4.2 Secondary estimand

Efficacy (i.e., 'du jure', 'hypothetical') estimand The efficacy estimand quantifies the average treatment effect of EPA-rich Omega-3 relative to placebo over 36 weeks, as an adjunct to the German S3 guideline standard of care, if all randomized subjects had adhered to the randomly assigned treatment for the entire trial duration.

5 Endpoints

5.1 Primary endpoints

- CDRS-R total score trajectories from baseline to week 36 (measured at baseline, 6, 12, 24, and 36 weeks)

5.2 Secondary endpoints

5.2.1 Confirmatory secondary endpoints

- Remission (CDRS-R total score less than or equal to 28) at any point during the 36 weeks of trial observation
- Response (30% reduction in CDRS-R total score) at any point within 12 weeks from baseline
- Participants newly initiating antidepressant medication (or newly increasing dose if on antidepressant at baseline) at any point during the 36 weeks of trial observation
- Number of days on trial before new antidepressant initiation (or new antidepressant dose increase if on antidepressant at baseline)
- KIDscreen-CAT-27 overall quality of life score at 36 weeks
- DIKJ depression score at 36 weeks

5.2.2 Supportive secondary endpoints

Effect endpoints

- Number of days in hospital
- Lower outpatient service use

Safety endpoints

- Suicidal ideation (SIQ-Jr) from baseline to week 36 (measured at baseline, 6, 12, 24, and 36 weeks)
- Number of SUSARs from baseline to week 36

Statistical considerations

6 Sample size determination

The sample size calculations were performed for the primary outcome, as well as closely related secondary outcomes in order to ensure all questions of high interest are sufficiently powered. All calculations assume a parallel two-arm design with a 1:1 randomization ratio.

6.1 CDRS-R Difference

Meta-analyses selecting studies of omega-3 fatty acids with high proportion of EPA in aMDD as primary diagnosis found an SMD between 0.28-0.56 (see Protocol references 160-166). However, no studies were performed in pMDD, except for one very small (n=20) pilot study in childhood depression with a large effect size (SMD=1.2) (see Protocol reference 167).

A two-sample t-test (equal variances) would require 74 participants per treatment arm to have 90% power to detect an optimistic standardized mean difference of 0.54 on the CDRS-R scale at the 0.05 two-sided significance level. The trial would then require a total of 148 participants.

As the placebo response rate in minors is probably higher compared to that reported in the single center RCTs in adults summarized in the meta-analyses referenced above, we calculated our sample size estimation under more conservative assumptions as well.

The sample size calculation above for testing a difference in CDRS-R scores considered a relatively optimistic effect size and did not account for loss to follow-up. A two-sample t-test (equal variances) would require 111 participants per treatment arm to have 80% power to detect a smaller standardized mean difference of 0.4 on the CDRS-R scale at the 0.05 two-sided significance level. The total sample size needed would then be 222 participants.

6.2 Difference in Proportion of Responders

A two-proportion z-test would require 97 participants per treatment arm to have 80% power to detect a difference in response of 20% (with 60% response in the treatment group and 40% response in the control group) at the 0.05 two-sided significance level. Accounting for a 10% loss to follow-up results in a total sample size of 216 participants.

7 Statistical analyses

Analysis sets The following analysis sets are defined in accordance with the ICH-E9 guidelines:

- The full analysis set (FAS) includes all randomized subjects. The FAS will be used for 'as randomized' evaluation. Only in exceptional cases may subjects be excluded from the FAS. In such cases the reason for exclusion will be justified and documented.
- The safety analysis set includes all randomized subjects receiving at least one dose of randomized treatment. The safety analysis set will be used for 'as treated' evaluation.

Baseline comparability of randomized groups Baseline descriptive variables of participants (including antidepressant use) will be summarized overall and by treatment arm using suitable measures of central tendencies and variability for continuous data (means or medians, SD or IQR) and frequencies and proportions for categorical data. No hypotheses are tested.

The number of participants lost to follow-up, initiating antidepressants, and adhering to the protocol will each be tabulated by treatment arm and visit. Baseline characteristics will also be summarized across the groups of participants completing the trial, lost to follow-up, and initiating antidepressant use.

General statistical considerations Statistical analysis results will generally be presented as point estimates with two-sided 95% confidence intervals. A limited number of analysis results will additionally be reported with p -values, which will be interpreted as indicative of superiority when the value is less than 5% and the estimated treatment contrast favors the omega-3 treatment arm.

Descriptive statistics for all efficacy and safety endpoints will be presented according to treatment arm.

The baseline values are collected at visit 1 (0 weeks), which is the first week after the lead-in phase. Further measurements are taken at visits 2 through 5 at 6, 12, 24, and 36 weeks.

The clinical trials registry number (03167307) will be used as a seed number, if needed.

Missing data By design, several baseline model covariates cannot be missing, as they are required for minimization during randomization. We distinguish between study dropouts and intervention dropouts. Study dropouts are participants whom withdraw consent, are monotone not available for follow-up visits, or are removed from the trial according to the protocol due to non-compliance (< 60% pills taken). Intervention dropouts are participants whom newly initiate an off-trial antidepressant or are newly prescribed an increased dose of an off-trial antidepressant prescribed before baseline.

Methods to handle missing data are outlined per analysis type below. Where multiple is used, 50 imputed datasets will be computed. Results across datasets will be combined using Rubin's rule.

Modeling In case of covariate imbalance on baseline covariates other than antidepressant use, omega-3 index, age, gender, and hsCRP, these covariates will also be included in the models described below. In case of computational convergence issues, simpler models will be estimated.

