11 STATISTICAL METHODS

Descriptive statistics will be provided for all data broken down by medication (omega-3 fatty acids and placebo), group (patients who recovered from the depression, patients who did not recover) and visit. Mean, median, standard deviation, range and number of observations will describe continuous variables. Frequencies and percentages will describe discrete variables. All statistical tests will be carried out two-tailed; the alpha (level of significance) is 5%. Efficacy of the treatment will be assessed using a linear random coefficient regression model.

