7.2 Secondary endpoints

7.2.1 Confirmatory secondary endpoints

The binary confirmatory secondary outcomes include:

- **Remission**, defined as a CDRS-R total score < 28 at any time up until 36 weeks
- **Response**, defined as a 30% drop in CDRS-R total score at any time up until **12 weeks**
- **Intervention dropout**, defined as initiation of non-randomized antidepressant use while on trial for participants not on a non-randomized antidepressant at baseline or an increase in antidepressant dose while on trial for participants on a non-randomized antidepressant at baseline

Unadjusted proportions per treatment arm will be presented with 95% confidence intervals. To adjust for baseline antidepressant use, omega-3 index, and CDRS score, as well as the minimization factors age, gender, and hsCRP, these binary outcomes will each be assessed using log-binomial models with treatment arm as the effect of interest. Each model will be interpreted in terms of the adjusted risk ratio (RR) comparing the outcome probability in the omega-3 group to that in the placebo group ($RR_{\text{omega-3/placebo}}$). The null hypothesis that the risk ratio is equal to 1 (no difference in risk across treatment groups) will be rejected if the 95% confidence interval for the risk ratio does not include 1. If the 95% confidence interval for the risk ratio is above 1, omega-3 treatment will be considered superior.

These models will include data from all randomized participants and analyze the participant data according to the treatment arms participants were randomized to (as-randomized). Data after intervention dropout will be considered missing. Multiple imputation under MAR will be used to impute longitudinal CDRS-R scores for study and intervention dropouts before the binary outcomes are determined. MI will be performed separately within each treatment arm (White et al 2011) using imputation models containing the minimization factors, baseline antidepressant use and omega-3 index.

As for the primary outcome, a delta-based sensitivity analysis approach will be used to address MNAR. For analysis of intervention dropout, imputation is only needed for participants with study dropout before intervention dropout and no sensitivity analysis is planned.

The continuous confirmatory secondary outcomes include:

- self-reported **quality of life** measured by the KIDscreen-CAT-27 overall score at 36 weeks
- **Depression severity** measured by DIKJ at 36 weeks

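### The SAP's superiority rule points the wrong way for antidepressant start, and its six confirmatory secondary endpoints are each tested at 5% with no order, alpha control or condition on the primary

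*SAP*

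**What the plan says.** - **Primary.** SAP section 2: "A single primary outcome, longitudinal CDRS-R total score, was selected". Section 7.1 reports one contrast for it, the treatment effect at 36 weeks.
- **Secondary tier.** SAP 5.2.1, headed "Confirmatory secondary endpoints", lists six: remission, response, antidepressant start or dose increase (yes/no), days to that event, KIDscreen-CAT-27 at 36 weeks and DIKJ at 36 weeks. A separate supportive tier follows in 5.2.2.
- **General rule.** Protocol section 11: "All statistical tests will be carried out two-tailed; the alpha (level of significance) is 5" per cent. SAP section 7 gives p-values, "which will be interpreted as indicative of superiority when the value is less than 5" per cent, and the same sentence adds a condition on direction: superiority is read only "when the value is less than 5% and the estimated treatment contrast favors the omega-3 treatment arm". Only some results will carry p-values, and the SAP does not list which.
- **Binary endpoints (SAP 7.2.1).** The ratio is omega-3 over placebo: "If the 95% confidence interval for the risk ratio is above 1, omega-3 treatment will be considered superior". The sentence covers remission, response and intervention dropout. The last is "defined as initiation of non-randomized antidepressant use while on trial", or a dose increase for those already on an antidepressant.
- **Continuous endpoints (SAP 7.2.1).** Direction is stated for each: interval above 0 for KIDscreen, below 0 for DIKJ.
- **Time to antidepressant (SAP 7.2.1).** Kaplan-Meier estimates and a log-rank test, with no superiority sentence.
- **Expected direction.** SAP section 1 describes antidepressant use "with greater antidepressant use hypothesized in the control arm". Protocol 5.2 (WH 2a) hypothesises the same.
- **Multiplicity.** Neither document gives an order, an alpha split or a condition on the primary. Protocol 11.2 lists the absence of adjustment among its sample size assumptions.

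**The concern.** There are two separate defects, and they have different consequences.

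The first is one of direction. A rule suited to favourable events (remission, response) is applied unchanged to an unfavourable one. Followed literally, it cannot recognise the benefit that the trial hypothesises for antidepressant use, and it would attach the word superior to the opposite result.

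The second is the status of the secondary claims. Calling endpoints confirmatory and giving them superiority rules invites formal claims. With no gate, such a claim could stand beside a failed CDRS-R result. This is a live issue here because protocol 11.1 still frames the main objective in terms of response rates, while the SAP has moved response to the secondary tier. Two of the six endpoints also describe the same event, once as yes/no and once as time.

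**Working it through.** **The plan's own figure first.** SAP 6.2 sizes response, one of the six, at an unadjusted two-sided 5%: 60% versus 40%, 80% power.

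n per arm = [1.96·√(2·0.5·0.5) + 0.8416·√(0.6·0.4 + 0.4·0.6)]² / 0.2² = (1.3859 + 0.5831)² / 0.04 = 96.9, so 97. With 10% loss, 97/0.9 = 107.8, so 108 per arm and 216 in total. Both figures reproduce.

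**Direction of the risk-ratio rule.** Three statements, side by side:

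1. SAP 7.2.1: omega-3/placebo ratio above 1 means superior, for all three binary endpoints.
2. SAP section 1 and protocol WH 2a: more antidepressant use is expected on placebo, so a ratio below 1 favours omega-3.
3. SAP section 7: superiority requires a contrast that favours omega-3.

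For intervention dropout, statement 1 contradicts 2 and 3.

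Illustration. The documents anticipate about 30% antidepressant use overall. Assume 110 per arm, 22.5% on omega-3 and 37.5% on placebo (average 30%), and use the normal approximation on the log ratio.

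- log(0.225/0.375) = −0.511
- SE = √[0.775/(110·0.225) + 0.625/(110·0.375)] = √0.04646 = 0.2156
- z = −2.37
- P(interval wholly below 1) = Φ(2.37 − 1.96) = 66%
- P(interval wholly above 1) = Φ(−2.37 − 1.96), about 0.001%

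With the rates swapped, so that omega-3 patients use more antidepressants, the rule as written declares superiority in 66% of trials.

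**Multiplicity.** Under no effect, a two-sided 5% test plus the favourable direction gives 2.5% false superiority per endpoint. For k independent endpoints, P(at least one) = 1 − 0.975^k:

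- k = 5 (the endpoints with an explicit superiority rule): 11.9%
- k = 6 (adding time to antidepressant under the general rule): 14.1%, with a Bonferroni ceiling of 6 × 2.5% = 15.0%

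The documents give no correlations, so these are assumed. Six endpoints, multivariate normal simulation, 1,000,000 draws, direction corrected:

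| Assumed common correlation | P(at least one false superiority claim) |
|---|---|
| 0 | 14.1% |
| 0.3 | 12.1% |
| 0.5 | 10.4% |
| 0.7 | 8.2% |
| 0.9 | 5.4% |

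Setting the two antidepressant endpoints at 0.9 changes the 0.5 and 0.7 rows to 9.8% and 7.9%.

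**Price of an alpha split.** Power for response at 97 per arm is Φ[(0.2·√97 − z·0.7071)/0.6928]:

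- two-sided 0.05 (z = 1.960): 80%
- 0.05/5 = 0.01 (z = 2.576): 58.5%
- 0.05/6 = 0.0083 (z = 2.638): 56.0%

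**The case against.** The other side has a fair case. The primary is a single outcome with one reported contrast, so the trial's main error rate is protected. Many trials leave secondary endpoints unadjusted. The general rule in section 7 already requires the contrast to favour omega-3, and the hypothesised direction of antidepressant use is clear, so the risk-ratio sentence can be read as a drafting slip. Time to antidepressant has no superiority rule of its own. Independence is implausible, since remission and response both come from the CDRS-R and DIKJ also measures depression.

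All of that stands, and it limits the point without removing it. The specific rule in 7.2.1 still contradicts the general one, and an analyst following it literally would reach the wrong conclusion. Leaving secondaries unadjusted is defensible; doing so while labelling them confirmatory and attaching superiority rules is not.

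Three stronger readings are tempting, and the documents do not support them:

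- A reader might infer a 26.5% error rate from 1 − 0.95⁶. That counts significant results in either direction under independence; its per-test comparator is 5%, and it is not a false superiority rate.
- A reader might infer that the reversed rule is what inflates false claims. Reversing a tail leaves that test's null rate at 2.5%. It raises the family rate only modestly, through correlation: at correlations of 0.5 and 0.7, with the antidepressant pair at 0.9, the rule as written gives about 11.6% and 9.9% instead of 9.8% and 7.9%.
- A reader might infer that the SAP commits to presenting harm as benefit. It does not: it contradicts itself, and its general rule and stated hypothesis point the right way.

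**Conclusion.** Both parts hold.

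The direction error is wrong as written and does not depend on any view about multiplicity. The 66% and 0.001% figures rest on the assumed 110 per arm and the assumed split of antidepressant use; the contradiction itself needs no assumption.

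The multiplicity point concerns the secondary claims only. With no true effects and the direction corrected, the chance of at least one false superiority claim is about 14% for six independent endpoints (11.9% for the five with explicit rules), about 8–10% at correlations of 0.5–0.7 and about 5% at 0.9, against 2.5% per test. Because positive correlation is likely, the independent figure should be read as the upper end of the range.

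**What to change.** **Direction.** In SAP 7.2.1, state that for intervention dropout superiority requires the 95% interval for the risk ratio to lie below 1, and keep above 1 for remission and response. This is one sentence and costs nothing.

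**Secondary claims.** Choose one of two routes in SAP 5.2.1 and 7:

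1. Test the confirmatory secondaries only if the primary is significant, in a prespecified fixed order, each at two-sided 5%, stopping at the first that fails. Count antidepressant start once: the sponsor chooses the binary or the time-to-event version as the tested endpoint, and the other is descriptive. This holds the chance of any false superiority claim, primary included, at or below 2.5%. The order must be set before treatment codes are linked to outcomes.
2. Drop the confirmatory label and the superiority rules, and report estimates with 95% intervals.

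The cost of route 1 is fewer formal secondary claims: none if the primary fails, and none after the first failure in the order. Holm or Bonferroni would also control the error, but at the first step power for response falls from 80% to about 56–58% at 97 per arm. A fixed order is therefore preferable in a trial sized partly on response.
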